8.4 Investigational Medicinal Product Blind Maintenance

This trial is an observer-blind trial. Assignment to IMP is known only to the responsible unblinded trial personnel/vaccine administrators at the trial sites. The subjects, data collectors (e.g., investigator) and data evaluators are blinded to the material administered. Randomization and IMP administration must be done by designated unblinded site staff who must not be involved with data collection of any sort including safety evaluation of the subject after administration of IMP.

All care must be taken to ensure that the unblinded reports and documents are shared only with unblinded personnel and properly stored in a secured area, accessible only by authorized personnel.

8.5 Unblinding Procedure

The IMP blind shall not be broken by the investigator unless information concerning the IMP is necessary for the medical treatment of a subject, or if a subject requests it. In the event of a medical emergency, if possible, the medical monitor should be contacted before the IMP blind is broken to discuss the need for unblinding.

For unblinding a subject, the IMP blind can be obtained by the investigator, by accessing the IWRS.

The L pharmacovigilance department must be notified as soon as possible if the IMP blind is broken by the investigator and the completed SAE form, if applicable, must be sent within 24 hours. The date, time, and reason the blind is broken must be recorded in the source document.

If any subject is unblinded, the subject should continue to be monitored for safety follow-up.

All subjects will be unblinded at their Day 365 visit.

8.6 Accountability and Destruction of Sponsor-supplied Investigational Medicinal Products, and Other Clinical Trial Materials

The investigator or designee must ensure that the sponsor-supplied IMP are used in accordance with the approved protocol and is administered only to subjects enrolled in the trial. To document appropriate use of sponsor-supplied IMP, the investigator must maintain records of all sponsor-supplied IMP delivery to the site, site inventory, administration and use by each subject, and destruction or return to the sponsor or designee.

The investigator must maintain 100% accountability for all sponsor-supplied IMPs and other CTM (including ancillary materials, as applicable) received and administered during their entire participation in the trial. Inventory, tracking and accountability forms will be maintained in the pharmacy files.

Prior to site closure or at appropriate intervals throughout the trial, before any IMP, or CTM are destroyed or returned to the sponsor or designee for destruction, a representative from the sponsor will perform CTM accountability and reconciliation.

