- 8) Per medical history, subjects with chronic active hepatitis B or hepatitis C infection, human immunodeficiency viruses type 1 or type 2 infection, acute polyneuropathy (such as Guillain-Barré syndrome), or chronic idiopathic demyelinating polyneuropathy; subjects whose hepatitis C antibody test is positive but whose viral loads are negative may be enrolled;
- 9) Acute illness, with or without fever at the time of planned vaccination;
- 10) History of hypersensitivity or serious adverse reactions to vaccines, such as anaphylaxis or angioedema, or any known allergies to any component of the IVX-121 and/or IVX-241 vaccine, or hypersensitivity to latex;
- 11) Abnormal function of the immune system resulting from clinical conditions including chronic administration of systemic corticosteroids (oral/intravenous/IM at a daily dose equivalent of >20 mg prednisone in a period of more than 14 days), or administration of immunosuppressive chemotherapy, biologics, or radiotherapy within the past 3 months prior to planned vaccination;

- 12) Subjects who have received treatment with immunoglobulins or other biologics, such as immunosuppressive therapies expected to modify immune responses to vaccination (including monoclonal antibodies [MAbs] for chronic underlying conditions) within the past 3 months prior to planned vaccination;
- 13) Trial Personnel as an immediate family or household member
- 14) For licensed vaccines:
 - a) Receipt of licensed inactivated vaccines (including seasonal influenza vaccine) within 14 days prior to trial vaccine administration on Day 0, or licensed replicating vaccines such as RNA or live-attenuated virus vaccines within 30 days prior to Day 0.
 - b) Receipt of licensed vaccines is permitted after completion of the Day 28 visit.
 - c) Receipt of any licensed COVID-19 vaccines is permitted if dosing regimen completed within 21 days prior to Day 0 or after completion of the Day 28 visit.

There may be instances when individuals meet all eligibility criteria except one that relates to transient clinical circumstances (e.g., fever or recent use of excluded medication[s] or vaccine[s]). Under these circumstances, eligibility for enrollment may be considered if the appropriate window for delay has passed, inclusion/exclusion criteria have been rechecked, and if the subject is confirmed to be eligible ([Section 7.4](#)).

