8.3 Randomization Code Creation and Storage

Randomization is conducted using an IWRS. The system ensures proper distribution of subjects across group assignments; treatment assignments known only to the responsible unblinded trial personnel/vaccine administrators at the study center. Subjects and the main study team and clinical staff will remain blinded for the duration of the study unless emergency unblinding is necessary.

Randomization information is stored in a secured area, accessible only by authorized personnel.

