10.2 Causality of Adverse Events

Relationship (causality) to the IMP will also be assessed by the investigator. The relationship of each AE to the IMP, including solicited systemic ARs (solicited local (injection site) reactions are considered as related by default) will be assessed using the following categories:

Related:	There is suspicion that there is a relationship between the IMP and the AE (without determining the extent of probability); there is a reasonable possibility that the IMP contributed to the AE.
Not Related:	There is no suspicion that there is a relationship between the IMP and the AE; there are other more likely causes and administration of the IMP is not suspected to have contributed to the AE.

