The main trial will remain blinded until database lock for the primary analysis at Day 365, except for subjects who will receive a letter with their treatment assignment at their Day 365 visit. Blinded Clinical Research Associates and the Blinded Clinical Lead will also be unblinded at the end of each Day 365 visit. The remaining team members will remain blinded until every subject has completed their Day 365 visit and the Day 365 database has been locked. At the time of primary analysis, the SYNTH blinded biostatistics team will become unblinded. For further details, reference the Unblinded Team Management Plan.

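### Protocol 8.5 lets the investigator open the code whenever a subject asks, against 8.3 and 8.4, and the SAP sets no specific handling for subjects unblinded before Day 365

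*Protocol*

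**What the plan says.** **Grounds for a break.** Protocol 8.5 bars the investigator from breaking the blind "unless information concerning the IMP is necessary for the medical treatment of a subject, or if a subject requests it". It sets no earliest date for a request, no approval step and no need for a reason. The advice to reach the medical monitor first is confined to medical emergencies. Protocol 8.3 is narrower: "Subjects and the main study team and clinical staff will remain blinded for the duration of the study unless emergency unblinding is necessary".

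**Who learns the arm.** Under 8.5, "the IMP blind can be obtained by the investigator, by accessing the IWRS". Protocol 8.4 states: "The subjects, data collectors (e.g., investigator) and data evaluators are blinded to the material administered". Protocol 10.2 adds: "Relationship (causality) to the IMP will also be assessed by the investigator". Sections 8.2 and 8.4 already provide separate unblinded site staff, who give the injection and take no part in assessment.

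**After a break.** Section 8.5 requires notice to pharmacovigilance, an entry in source showing when and why the code was opened, and continued safety follow-up. It does not mention a replacement assessor.

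**The SAP.** Section 4.4 says: "The main trial will remain blinded until database lock for the primary analysis at Day 365, except for subjects who will receive a letter" giving their assignment at that visit. Blinded monitors and the blinded clinical lead are unblinded at the end of each Day 365 visit. Section 6.1.3 puts every dosed subject in the Safety Set and uses that set for all safety endpoints. Section 6.1.5 leaves exclusions from the Per Protocol Set (PPS) to a blinded review with a sponsor decision. Section 11.1.1 ends time at risk at last contact or first LRTI.

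**The concern.** The trial is observer-blind, so the assessor's ignorance of the arm is the feature that protects its subjective endpoints. As 8.5 is written, a well subject with no medical need can have that feature removed, and the person who opens the code is the one who judges causality.

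From then on, several records can depend on the known arm: whether the subject seeks care and reports it (MAAEs), whether the investigator calls an event related, and whether symptoms are reported early enough to lead to a visit and a nasopharyngeal swab (LRTI/CESI). The last of these also feeds the exploratory vaccine-efficacy estimate. If the SAP treats this follow-up as blinded, a reader of the report cannot tell how much of the comparison was blinded in fact.

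**Working it through.** The plan gives no figure for early unblinding, so there is none to reproduce. The check is a comparison of text, followed by simple arithmetic on size.

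1. **Can a site follow both rules?** Take a well subject who asks for the allocation midway through follow-up. Under 8.5 a request is a sufficient ground. Under 8.3 the subject "will remain blinded for the duration of the study unless emergency unblinding is necessary", and there is no emergency. One section permits the break and the other forbids it.

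2. **How many people are unblinded?** The route in 8.5 runs through the investigator's own IWRS access. That person is a blinded data collector under 8.4 and the causality assessor under 10.2. One request therefore unblinds two people.

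3. **What does the SAP then do with this subject?**
   - *Safety (6.1.3, 10.1):* the subject stays in the Safety Set and all events to the end of the main trial are counted. No flag, listing or censoring for early unblinding is named.
   - *Efficacy (11.1, 11.1.1):* the analysis uses the PPS, and person-time runs on past the break.
   - *PPS review (6.1.5, 6.3):* the sponsor could exclude the subject or later visits. But 6.3 defines a deviation as a failure to keep to the protocol, and 8.5 permits this break, so it is not clearly a deviation.
   - *Changes from protocol (12):* nothing on this point.

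4. **Which endpoints are exposed?**

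| Endpoint | Window | Depends on subject or assessor knowing the arm? |
|---|---|---|
| Solicited reactions | Day 0–6 | Yes, but the window is short |
| Unsolicited AEs | Day 0–28 | Yes, but the window closes at Day 28 |
| Antibody titers | Days 28, 180, 365 | Largely no (laboratory) |
| MAAEs | to Day 365 | Yes (care-seeking and reporting) |
| Causality of events collected after Day 28 | to Day 365 | Yes (investigator judgment) |
| LRTI/CESI, vaccine efficacy | to Day 365 (efficacy from Day 14) | Partly (symptoms lead to visit and swab, then RT-PCR) |

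5. **Size per subject.** Planned arms are 100, 100 and 50 (protocol 13.4). One unblinded placebo subject is 1/50 = 2% of the comparator; one vaccinee is 1/100 = 1% of that arm.

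6. **Share of main-trial follow-up left open for that subject.** For a break on day *d* the share is (365 − *d*)/365. The days below are scheduled contacts, chosen only to show the range:
   - *d* = 90: 275/365 = 75%
   - *d* = 180: 185/365 = 51%
   - *d* = 270: 95/365 = 26%

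The documents do not say how many subjects asked, or when, so no total and no bias can be calculated.

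**The case against.** - **Breaks are documented.** True: 8.5 requires a source record and notice to pharmacovigilance. It would be wrong to infer that early breaks are invisible. Traceability is not analysis handling, but it makes the handling feasible.
- **The PPS review is a route.** It is, and it reaches the efficacy analysis. It is discretionary, does not name unblinding, and does not reach the Safety Set. SAP 4.4 also refers to an Unblinded Team Management Plan that is not among the documents; it may say more.
- **The outcomes are fairly robust.** CESI needs RT-PCR confirmation and is derived by program, the symptom survey is prompted in every arm, efficacy is exploratory and no hypothesis is formally tested. All of this limits the harm. It does not remove the dependence of swabbing on reported symptoms, or of MAAEs on care-seeking.
- **The co-primary safety endpoints.** A reader might infer that these are compromised. Section 8.5 would allow a request in the first month, but the two windows close at Day 6 and Day 28 and nothing in the documents points to requests that early.
- **Licensed RSV vaccines.** A reader might infer that their approval would lead many placebo subjects to ask, and then to cross over. The documents give no request rate. The licensed-vaccine rule in 7.2, "Receipt of licensed vaccines is permitted after completion of the Day 28 visit", applies to everyone whether or not the arm is known, so taking a licensed vaccine does not require unblinding.
- **Wording.** The 8.5 clause is loosely built and could be parsed as forbidding a break on request. The ordinary reading is a second exception; the ambiguity is itself a reason to reword it.

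**Conclusion.** The contradiction between 8.5 on one side and 8.3 and 8.4 on the other is explicit, and following 8.5 as written unblinds an assessor whom the design requires to be blind. The analysis gap is real but limited: no rule for the Safety Set, no end to efficacy person-time at unblinding, and only a discretionary review for the PPS.

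The size is 2% of the comparator for each placebo subject affected, times a number that the documents do not give and that may be zero. The exposure lies mainly in the post-Day 28 safety and respiratory-illness data. The conclusion rests on reading the request clause as a free-standing ground and on there being no further rule in documents not available here. It does not support a claim that the immunogenicity results or the primary safety results are biased.

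**What to change.** **Protocol.** Reconcile 8.3 and 8.5 so that a non-medical request does not unblind the assessor, for example by passing it to the unblinded site staff already in place under 8.2 and 8.4. Leave the medical-need route unchanged. Holding requests until Day 28 would serve no purpose: protocol version 5.0 already reports the Day 28 interim results.

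**SAP.** This part matters most for the present trial, since the SAP was written after the October 2024 notice that the extension had been discontinued.
- List every subject unblinded before Day 365, by arm, with date and reason taken from the source record that 8.5 already requires.
- Repeat the MAAE, CESI and vaccine-efficacy summaries with data censored at the unblinding date: count only events that began before it, and end person-time there.
- Present these as sensitivity analyses beside the planned ones, because subjects who ask may differ from those who do not and censoring them assumes otherwise.

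**Cost.** One protocol clarification, one listing and one sensitivity analysis, with dates retrieved from source if they are not in the database. If nobody asked, the listing is empty and shows that no code was opened early. A subject told by unblinded staff may still disclose the arm to the investigator, so the leak is reduced, not removed.

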9.0 TRIAL PLAN

9.1 Trial Procedures

The following sections describe the trial procedures and data to be collected. The time and events schedules for the main trial and for the extension are located in [Section 2.1](#) and [Section 2.2](#), respectively. All procedures must be performed by qualified and trained staff.

9.1.1 Informed Consent and Eligibility

The requirements of the ICF are described in [Section 15.2](#).

Informed consent must be obtained before any protocol-directed procedures are performed.

A unique subject number is assigned to each subject after informed consent is obtained. If all eligibility criteria are fulfilled and the subject is randomized, this subject number is used throughout the trial. Subject numbers assigned to subjects who are not randomized should not be reused.

IVX-A12a and placebo recipients must sign a second consent if they agree to participate in the trial extension period.

9.1.2 Demographics, Medical History and Medication History

Demographic information to be obtained will include age/date of birth (if applicable), sex, race (and ethnicity) as described by the subject.

Medical history is also collected, including but not limited to any medical history that may be relevant to subject eligibility for trial participation such as prior vaccinations, medication history, concomitant medications, and previous and ongoing illnesses and/or injuries. Relevant medical history can also include any medical history that contributes to the understanding of an AE that occurs during trial participation if it represents an exacerbation of an underlying disease/pre-existing problem. Information about the subject's makeup and interactions with people of different age groups is collected. History of the use of alcohol, tobacco, and marijuana will also be collected.

Medical history (including corresponding medication) to be obtained includes any significant conditions or diseases that have disappeared or resolved at or prior to signing of the ICF.

Adverse medical occurrences emerging during the time between signing of the ICF and the administration of IMP are recorded in the AE electronic case report form (eCRF). If such an adverse medical occurrence is assessed as related to a screening procedure this should be recorded as an AE related to trial procedure in the eCRF.

All medications, vaccines and blood products taken or received by the subjects are collected as prior and concomitant medications ([Section 7.2](#)):

- a) Medications: 1 month prior to screening.
- b) Vaccines: 1 year prior to screening for any investigational, for any non-registered vaccines and for any licensed vaccines.
- c) Blood products: 3 months prior to screening.

The use of antipyretics and/or analgesic medications within 24 hours prior to vaccination must be identified and the reason for their use (prophylaxis versus treatment*) must be documented. Administration of the IMP should be delayed by 24 hours.

*Medications taken for prophylaxis are those intended to prevent the onset of AEs following vaccination. Medications taken for treatment are intended to reduce or eliminate the presence of symptoms that are present.

Assess and record concomitant therapy (prescription medications ONLY) and vaccine history as described above in the source documents.

See [Section 9.2.8](#) for recording of medications during the trial extension, i.e., 12-month observational follow-up.

9.1.3 Documentation of Trial Entry/Randomization

If the subject is ineligible for randomization, the investigator should record the primary reason for failure on the subject screening and enrollment log using the following categories:

- Screen failure (did not meet one or more inclusion criteria or did meet one or more exclusion criteria);
- Withdrawal by subject;
- Enrollment target reached;
- Trial terminated by the sponsor.

Subject numbers assigned to subjects who fail screening cannot be reused.

In the event of major protocol violations/ deviations (such as failure to collect Day 0 samples for serology or safety analyses) occurring during the active phase of entry/randomization leading to dosing of eligible subjects, replacement of an approximate equal number of subjects is allowed.

9.1.4 Physical Examination

Physical examinations must be performed by a qualified health professional in accordance with local regulations and as listed within the site responsibility delegation log. A complete physical exam is performed at screening according to the following schedule:

Visit	Physical Examination Components
Screening	Full physical examination including vital signs, blood pressure, heart rate, respiratory rate, oxygen level (SpO ₂), weight, and height.
Day 0	Full physical examination including vital signs, blood pressure, heart rate, respiratory rate, oxygen level (SpO ₂), weight, and height.
Day 28	Full physical examination including vital signs, blood pressure, heart rate, respiratory rate, oxygen level (SpO ₂), weight, and height.
Day 180	Full physical examination including vital signs, blood pressure, heart rate, respiratory rate, oxygen level (SpO ₂), weight, and height.
Day 365	Full physical examination including vital signs, blood pressure, heart rate, respiratory rate, oxygen level (SpO ₂), weight, and height.
Day 770 (Trial Extension)	Full physical examination including vital signs, blood pressure, heart rate, respiratory rate, oxygen level (SpO ₂), weight, and height.

Symptom-directed physical examination may be performed at subsequent visits if deemed necessary.

9.1.5 Vital Signs

A subject will have their vital signs measured at the screening visit, prior to dosing, and at all regularly scheduled clinic visits, including body temperature, blood pressure, heart rate, respiratory rate, oxygen level (SpO₂), weight (at screening only) and height (at screening only). Follow standard of care for trial population and operational feasibility. SpO₂ will not be performed during the trial extension unless clinically indicated.

9.1.6 Immunogenicity Assessments

Blood sampling for immunogenicity is taken at Days 0, 28, 180, and 365, and for the trial extension population subset at Day 770. All subjects are followed for persistence of antibody responses through the entire duration of the clinical trial (approximately 12 months), and then antibody responses will be checked in the trial extension subset at Day 730. All samples must be collected in accordance with acceptable laboratory procedures.

In the event of local or national health related closures and limited ability for travel (e.g., as a consequence of SARS-CoV-2 circulation), the clinic may default to their institution guidelines to continue follow-up assessments with subjects as necessary.

The assays are described in [Table 3](#). Refer to [Table 5](#) for maximum volume of blood collected at any single visit.

Table 3 Phase 2a Core Clinical Bioanalytical Assays

Assay	Purpose	Comment
RSV neutralization (RSV/A, RSV/B)	1° and 2° immunogenicity endpoints	Neutralization titers define magnitude of functional immune response to RSV/A and RSV/B
hMPV neutralization (hMPV/A, hMPV/B)	1° and 2° immunogenicity endpoints	Neutralization titers define magnitude of functional immune response to hMPV/A and hMPV/B
RSV pre F protein binding ELISA	1° and 2° immunogenicity endpoints	Total IgG response for use in analysis of quality metric as defined by relative rise in $\frac{IgG_{post}}{IgG_{pre}}$ * $\frac{IgG_{post}}{IgG_{pre}}$
hMPV pre F protein binding ELISA	1° and 2° immunogenicity endpoints	Total IgG response for use in analysis of quality metric as defined by relative rise in $\frac{IgG_{post}}{IgG_{pre}}$ * $\frac{IgG_{post}}{IgG_{pre}}$
Anti-VLP core IgG ELISA (VLP Core)	Exploratory endpoint	Analysis of response to VLP core (without DS-Cav1 antigen) after vaccination to inform platform technology, interpretation of safety and immune responses to DS-Cav1 antigen.
BioFire Respiratory Panel 2.1 (RP.1)	2° safety endpoint and exploratory efficacy endpoint	Diagnostic assay to detect and identify nucleic acid targets in respiratory specimens from virological agents that cause the RSV and/or hMPV respiratory infection (and other agents).

Abbreviations: ELISA, enzyme-linked immune absorbent assay; IgG, immunoglobulin G; hMPV, human metapneumovirus; RSV, respiratory syncytial virus; VLP, virus-like particle.

Serological samples will be assessed for primary or secondary immunogenicity endpoints using the following assays:

- RSV/A-specific and hMPV/A-specific NAb assay;
- RSV/B-specific and hMPV/B-specific NAb assay;
- Anti-RSV and anti-hMPV Pre F protein-specific IgG ELISAs.

CCI

[figure not shown]
The anti-RSV Pre F protein IgG ELISA and anti-hMPV Pre F protein IgG ELISA have been qualified for the quantification of binding IgG antibodies to the Pre F protein in human serum samples.

Serological samples will be assessed for exploratory immunogenicity endpoints using the following assays:

- Anti-VLP core IgG ELISA.

An anti-VLP core ELISA was qualified for the quantification of binding IgG antibodies to VLP core in human serum samples.

CCI

